5.7. Data analysis

Sample size

A recent randomized, controlled, peer-to-population trial testing similar dietary approaches to reduce SFA intake showed a long-term change in LDL-C of approximately 15 mg/dL (SD26).¹⁹ If 78 participants are recruited in each group ($n = 156$), it is expected to detect a minimum difference of 15 mg/dl between the intervention group and the control, with a power or detection capacity of 90%, an error $\alpha = 0.05$ and a dropout rate of 20% using intention-to-treat analysis, so the final sample size includes an additional 20% of participants to mitigate dropouts.

Statistical analysis of primary and secondary outcomes

Baseline characteristics will be summarized in descriptive statistics in each study group, statistical analysis will be performed with STATA IC 16.0 software (College Station, TX: StataCorp LLC 2019). Descriptive statistics will be presented with standard deviation (SD) and 95% confidence intervals. Continuous variables will be presented as mean and standard deviation unless the use of the median and interquartile range is necessary; Categorical variables will be expressed as frequencies and percentages.

Efficacy results will be analysed by intent to treat, i.e., all participants will be assessed according to the group to which they are randomly assigned, regardless of their adherence. The analysis of effectiveness measures will use data from all participants for whom a baseline and monitoring measure exists. A linear regression model will be used to calculate the difference in measures with 95% confidence intervals, with adjustment of the initial values of the dependent variable and the place of recruitment. Before the analysis, the assumptions of linear regression, specifically homoscedasticity and the normality of the residual distribution, will be explored. Where these assumptions are not met, appropriate non-parametric analyses shall be used. The sensitivity of the results to confounders due to

differences in baseline characteristics will also be examined. A second sensitivity analysis will use the techniques of "baseline observation carried forwards" (using the initial measure of the variable) and "multiple imputation" (using information about the assigned group and the characteristics of the participants) to impute missing values in the variables of the main outcome. An exploratory analysis of subgroups of results will be carried out according to sociodemographic characteristics.

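### Adding 20% does not offset a 20% loss: 78 per arm keeps 90% power only up to about 17% dropout, and unadjusted power at 20% dropout is about 89%

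*Protocol*

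**What the plan says.** The sample-size paragraph of Protocol section 5.7 takes its inputs from an earlier trial that "showed a long-term change in LDL-C of approximately 15 mg/dL (SD26"). With 78 participants per group (156 in total), "it is expected to detect a minimum difference of 15 mg/dl between the intervention group and the control", at 90% power and alpha 0.05. Dropout enters as "a dropout rate of 20% using intention-to-treat analysis", and the paragraph ends "so the final sample size includes an additional 20% of participants to mitigate dropouts".

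Two later statements in the same section bear on this. On who is analysed: "The analysis of effectiveness measures will use data from all participants for whom a baseline and monitoring measure exists". On the model, a linear regression is planned "with adjustment of the initial values of the dependent variable and the place of recruitment". Baseline carried forward and multiple imputation appear only as sensitivity analyses.

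The number of completers needed before the dropout allowance is not written down.

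**The concern.** To be left with n completers after losing a fraction d, one must recruit n/(1 − d). Recruiting n × (1 + d) falls short, because the loss applies to the larger recruited number. The wording of the allowance suggests the second formula, and the figure of 78 fits it.

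If so, the stated power and the stated dropout rate cannot both be right for the calculation described. At stake is a declared design property. A reader who repeats the sum from the protocol's own inputs will not obtain it, and the same pair of figures may be carried into later reports of the trial.

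**Working it through.** **Inputs.** All are from section 5.7 except the 1:1 allocation, which is in section 5.4: difference 15 mg/dL, SD 26 mg/dL, alpha 0.05, power 90%, dropout 20%, 78 per arm. Sidedness is not stated; I take two-sided. A one-sided test needs 52 per arm, which becomes 63 (× 1.2) or 65 (÷ 0.8), and neither gives 78.

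**Step 1: completers needed.**
- Normal approximation: n = 2 × (1.960 + 1.2816)² × (26/15)² = 63.14, so 64 per arm.
- t-test (noncentral t): 64 per arm gives 89.95% and 65 gives 90.4%, so 65 per arm.

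**Step 2: reproduce the stated 78.**
- 65 × 1.2 = 78.0, so N = 156. This matches exactly.
- 64 × 1.2 = 76.8, so 77 per arm.
- 65 / 0.8 = 81.25, so 82 per arm (N = 164).
- 64 / 0.8 = 80 per arm (N = 160).

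The plan's figure is therefore the t-test size multiplied by 1.2. The 65 is my reconstruction, but the conclusion does not depend on it: by the normal approximation, correct inflation still gives 80, above 78.

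**Step 3: what 20% dropout leaves.** 78 × 0.8 = 62.4 per arm, or 156 × 0.8 = 124.8 in total, which is about 62 + 63.

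**Step 4: unadjusted power by dropout, starting from 78 per arm (t-test).**

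| Dropout | Analysed per arm | Power |
|---|---|---|
| 0% | 78 | 94.7% |
| 10% | 70 | 92.4% |
| 15% | 66 | 90.8% |
| 16.7% | 65 | 90.4% |
| 20% | 62 | 89.0% |

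With 62 + 63 analysed, power is 89.2%. By the normal approximation it is 89.5% at 62 per arm and 89.7% at 62 + 63.

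**Step 5: dropout tolerated at 90% power.** 1 − 65/78 = 16.7% (t-test), or 1 − 64/78 = 17.9% (normal approximation). Put the other way, the difference detectable with 90% power at 62 per arm is 15.3 mg/dL rather than 15.

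**Step 6: effect of the planned baseline adjustment at 62 per arm.** The protocol gives no baseline to follow-up correlation r, so these values are assumptions. It also does not say which SD the 26 is.
- If 26 is the SD of follow-up values, the residual SD is 26 × √(1 − r²). Power reaches 90% at r of about 0.18, and r = 0.3 gives 91.6%.
- If 26 is the SD of change (equal SDs at both visits), the residual SD is 26 × √((1 + r)/2). Power is at least 90% for r up to about 0.93, and r = 0.8 gives 91.9%.

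**The case against.** The strongest reply is that the 89% belongs to an analysis the protocol does not plan. The primary model adjusts for baseline, and over most plausible correlations (step 6) that model has at least 90% power with 62 per arm. The gap is also close to rounding: with 125 completers the normal approximation gives 89.7%, which rounds to the stated 90%. The method is disclosed, since the text says 20% was added, and nothing in the conduct or analysis of the trial would change.

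Much of this stands. The effect on the trial is minor, and the trial should not be called underpowered. It does not make the statement correct. The sample-size paragraph claims no gain from adjustment and gives no correlation, so the margin is unstated. Under the calculation it does describe, power at 20% dropout is below 90% by either method.

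A second reply is that intention-to-treat keeps dropouts in. Here it does not: the main efficacy analysis requires both a baseline and a follow-up value, and imputation is confined to sensitivity analyses.

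**Conclusion.** The concern holds, as a small but definite arithmetic error. With 78 recruited per arm, the protocol's inputs give 90% power at up to 16.7% dropout (17.9% by the normal approximation). At 20% dropout they give 89.0% to 89.2% by t-test, or 89.5% to 89.7% by the normal approximation. Against correct inflation, recruitment is 4 per arm short (2 by the normal approximation); against the 65 needed, about 3 completers per arm are missing.

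This rests on a two-sided test, on an unadjusted comparison with SD 26, and on dropouts having no follow-up LDL-C. The planned adjustment probably restores 90% in practice, but that depends on a correlation the protocol does not give.

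**What to change.** Keep N = 156 and rewrite the sample-size sentence in section 5.7 in one of three ways:

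- **(a)** State that 78 per arm, leaving 62 after 20% dropout, gives about 89% power for a between-group difference of 15 mg/dL with SD 26.
- **(b)** Keep 90% power and state the tolerated dropout as 16.7%.
- **(c)** Base the 90% on the planned baseline-adjusted model, and state the assumed baseline to follow-up correlation with its source.

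As a side clarification in the same sentence, say whether SD 26 refers to change or to follow-up values, and whether the earlier trial's 15 mg/dL was a between-arm difference. Option (c) cannot be checked without the meaning of the SD.

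The cost is one sentence, with no extra participants and no change to the analysis. Under (a) or (b) the stated power or dropout tolerance becomes slightly less favourable. If the sponsor prefers to keep both 90% and 20% on the unadjusted calculation, the price is 82 per arm (N = 164, 8 more participants), which a gap this small does not seem to justify.

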5.5. Randomization

Randomization will be computer-generated, with sex, age, obesity, and diet (fiber intake) as stratification variables using random blocks of size 2 and 4. The computer program will reveal the group assigned at the same time to the researcher, without the option of viewing the groups that will be assigned to future patients.

It will not be possible to blind patients to the intervention group due to the nature of the intervention; however, the primary outcomes of efficacy measures will be objectively measured (blood lipids) and are not subject to interpretation by investigators. To the extent possible, the study team performing all measurements will remain blind to group assignment during the study.

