5.6. Definition of variables: main and secondary results

With the determinations and measurements derived from the CADIMED study, it is proposed to investigate the following results (comparing the intervention group and the control group):

- 1) Main results: changes in LDL-C and fatty acid profile in erythrocytes after 8 weeks of intervention
- 2) Secondary outcomes:
 - a. Changes in other metabolites derived from lipid and metabolomic profile analysis, including circulating fatty acids, HDL-C, total cholesterol, triglycerides, and endogenous and exogenous metabolites related to cardiovascular risk and meat consumption (e.g., TMAO, etc.);
 - b. Changes in other related markers of cardiovascular risk, including biomarkers of inflammation and endothelial damage, insulin resistance, and diabetes (glucose, insulin, HbA1c, C-reactive protein, IL6, TNF-alpha), blood pressure, weight, and body and waist mass index;

- c. Changes in the gut microbiota and derived metabolites
- d. Changes in dietary intake (measured by 24-h recall): SFA intake, total energy intake, total fat, sugar, fiber, salt, general dietary patterns, red and processed meat consumption.
- e. Changes in other lifestyle-related factors: collected through physical activity, smoking, and alcohol questionnaires

3) **Evaluation of the process**: analyses of both quantitative and qualitative measures will be included to understand whether the intervention has worked and through which processes. These measures include: the rate of recruitment of volunteers and the rate of patients completing the study; acceptance of the intervention through questionnaires at the end of follow-up; the use of the mobile application to carry out changes in the diet as well as the self-monitoring of intake; measures that evidence the contamination of the control group; changes in patients' ability and knowledge about diet, SFA, and cardiovascular disease.

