To make it easier to remember, initially write down the menu consumed at each meal and then describe the ingredients in detail. To help memory, it is practical to remember where you ate, with whom, at what time, who prepared the meal, etc; These details will help you "get into the situation."

Has the food you're about to record been different for any reason?

Yes No

If yes, please indicate why:

Indicate if you take supplements (type and amount):

Date corresponding to the day of remembrance:	
Breakfast	
Menu (food and preparation)	Ingredients (type and quantity)
Drinks:	
Sugar:	
Mid-morning	
Menu (food and preparation)	Ingredients (type and quantity)
Food	
Menu (food and preparation)	Ingredients (type and quantity)

 • First • Second • Dessert 	
Drinks:	
Bread:	
Oil (Type):	
Snack	
Menu (food and preparation)	Ingredients (type and quantity)
Dinner	
Menu (food and preparation)	Ingredients (type and quantity)

 • First • Second • Dessert 	
Drinks:	
Bread:	
Oil (Type):	
Between meals	
Menu (food and preparation)	Ingredients (type and quantity)

LOG OF PROTOCOL CHANGES

Version	Date	Changes
1.0	11 November 2022	
1.1	3 February 2023	
 1. Inclusion of the SAS nursing team 2. Size of the randomization blocks: change from 8 and 16 to 2 and 4 due to the improvement in the balance and distribution of characteristics in the intervention groups 3. Inclusion of sensitivity analyses: baseline observation carried forwards (using the initial measure of the variable) and multiple imputation (using information about the assigned group and the characteristics of the participants) to impute missing values in the variables of the main outcome

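### Randomisation is stratified by sex, age, obesity and fibre intake, but the primary regression adjusts for none of them, so the confidence interval may be wider than the design warrants

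*Protocol*

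**What the plan says.** Section 5.5 generates the allocation "with sex, age, obesity, and diet (fiber intake) as stratification variables using random blocks of size 2 and 4". The log of protocol changes for version 1.1 records that the blocks were reduced to these sizes "due to the improvement in the balance and distribution of characteristics in the intervention groups".

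Section 5.7 sets the efficacy analysis as a linear regression that yields the between-group difference and its 95% interval. That model is fitted "with adjustment of the initial values of the dependent variable and the place of recruitment". Place of recruitment is not among the stratification factors, and none of the four stratification factors is among the covariates.

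The only other adjustment is a sensitivity analysis. It begins "The sensitivity of the results to confounders due to" and ends "differences in baseline characteristics will also be examined". It names no covariates.

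**The concern.** Stratified blocks force the arms to be similar on the chosen factors. Where those factors are prognostic, chance imbalance on them no longer contributes to the variance of the treatment difference. A regression that omits them still counts their contribution as residual noise, so its standard error is too large for the design that was run. The 95% interval over-covers, the test is conservative, and the precision that the stratification and the smaller blocks were meant to provide goes unused.

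The section 5.7 sensitivity analysis does not repair this. It is prompted by baseline differences, which stratification tends to remove for exactly these factors, and it leaves the primary interval and p-value unchanged.

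This is not a detail left to a later analysis plan. The protocol itself lists the covariates, so an analysis plan that followed it would carry the mismatch forward, and one that did not would contradict it.

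**Working it through.** **Inputs from the protocol (5.4, 5.5, 5.7):** difference 15 mg/dL, SD 26, alpha 0.05, power 90%, dropout 20%, 78 per arm, 1:1 allocation, blocks of 2 and 4.

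**Assumed, because the protocol does not give them:** the number of levels per factor, three recruitment places, and R², the share of outcome variance that the four factors explain after adjustment for baseline. SD 26 is taken as the residual SD after baseline adjustment.

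**1. The plan's own figure.** Two-sided normal approximation: n = 2(1.96 + 1.2816)² × 26² / 15² = 63.1, so 64 per arm. The t-test version gives 65, and 65 × 1.2 = 78, as stated. After 20% dropout, 78 × 0.8 ≈ 62 per arm remain. SE = 26 × √(2/62) = 4.67, and power = Φ(15/4.67 − 1.96) = 89.5%. The sample size reproduces.

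**2. What theory predicts.** With perfect balance on the factors, the true variance falls by the factor (1 − R²) while the model that omits them still reports the full SD. Its actual type I error is then 2[1 − Φ(1.96/√(1 − R²))]: 3.9% at R² = 10% and 2.8% at 20%. Dropout and incomplete blocks make the balance imperfect, so the real effect is somewhat smaller.

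**3. Simulation of the actual design.** 8,000 trials per scenario, 156 patients, stratified blocks of 2 and 4, 20% random dropout. Sixteen strata means two levels per factor; 54 means three levels each for age, obesity and fibre. Monte Carlo SE is about 0.2 points for type I error and 0.4 points for power.

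| Strata | R² | Protocol model: mean SE | Empirical SD | Type I error | Power, protocol model | Power, four factors added |
|---|---|---|---|---|---|---|
| 16 | 0% | 4.72 | 4.74 | 5.2% | 87.8% | 87.3% |
| 16 | 5% | 4.72 | 4.62 | 4.4% | 88.3% | 89.1% |
| 16 | 10% | 4.72 | 4.52 | 3.9% | 89.3% | 91.3% |
| 16 | 20% | 4.71 | 4.35 | 3.0% | 89.9% | 94.0% |
| 54 | 0% | 4.72 | 4.74 | 5.0% | 88.1% | 87.2% |
| 54 | 5% | 4.71 | 4.65 | 5.0% | 88.6% | 89.1% |
| 54 | 10% | 4.72 | 4.56 | 4.3% | 89.3% | 91.0% |
| 54 | 20% | 4.72 | 4.39 | 3.8% | 89.5% | 93.6% |

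The excess in the standard error is the ratio of the third column to the fourth. At R² = 10% it is 4.72/4.52 = 1.04 and 4.72/4.56 = 1.04; at 20% it is 4.71/4.35 = 1.08 and 4.72/4.39 = 1.08. Repeat runs of the same design gave about 2 to 4% and 6 to 7%. With the four factors included, model SE and empirical SD agree (4.49 and 4.48 at 10%, 4.24 and 4.21 at 20%, 16 strata), and type I error is 4.8 to 5.1% at R² of 10% and 20% for both numbers of strata.

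**4. Coverage and width.** A further 6,000 trials per setting, with two-level factors and no place term, gave coverage of 96.4% at R² = 10% and 96.7% at 20% when the factors were omitted, against 95.4% and 94.8% when included. Mean interval width fell from 18.5 to 17.6 mg/dL at 10% and from 18.5 to 16.6 mg/dL at 20%.

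**5. Palmitic acid.** The protocol gives no effect size or SD for it. The percentage excess in the standard error does not depend on the scale, so it carries over at the same R².

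**The case against.** The primary result is valid as written. The estimate is unbiased, type I error is not inflated, and power stays near the planned figure, so this is lost efficiency and not a threat to validity. That stands in full.

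The size rests on an R² that the protocol does not supply. It is R² beyond the outcome's own baseline, which may already carry much of what sex, age or obesity say about LDL-C. At 5% the gain is only 0.8 points (16 strata) or 0.5 points (54 strata), and with 54 strata no conservatism is visible. The benefit is clear only from about 10%. This also stands, and is why the point is put conditionally.

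SD 26 is quoted in section 5.7 for a change in LDL-C. If it is the SD of change, and the variances at the two visits are equal, baseline adjustment lowers the residual SD to 26√((1 + r)/2), where r is the correlation between visits: about 24 at r = 0.7 and 22.5 at r = 0.5 (r is assumed). The power gain then shrinks to roughly 0.5 to 3 points, because power is already higher. The percentage excess in the standard error does not change.

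Finally, the sensitivity analysis and the multiple imputation both draw on participant characteristics. Neither names the stratification factors or alters the primary model, so they soften the point without answering it.

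**Conclusion.** The mismatch is plain in the text: four factors govern the allocation and none enters the primary model. Its consequence is conditional and conservative. If the factors explain 10 to 20% of the variance left after baseline, the reported standard error is about 2 to 8% too large, and about 2 to 4 points of power are forgone at residual SD 26 (roughly 0.5 to 3 at residual SD 22.5 to 24). If they explain nothing, omitting them does no harm, and including them costs 0.5 to 0.9 points. These figures rest on assumed values for R², the number of factor levels and the number of recruitment places.

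The change is worth making. The possible gain exceeds the possible cost, the plan's own basis gives 89.5% power with no margin over 90%, and naming the factors in advance removes any later choice between adjusted and unadjusted results.

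**What to change.** In section 5.7, state the primary model as a linear regression of the week-8 value on randomised group, the baseline value of the outcome, place of recruitment, and sex, age, obesity and fibre intake. Enter the last four as main effects, in the categories used by the randomisation program, without stratum indicators or interactions, so that sparse strata cause no difficulty.

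Use the same model for the other continuous outcomes, with one simplification where the outcome is a stratification variable or close to it. Section 5.6 lists such outcomes among "SFA intake, total energy intake, total fat, sugar, fiber, salt" and "blood pressure, weight, and body and waist mass index". For fibre intake, the baseline value can replace the fibre category; for weight, BMI and waist, it can replace the obesity category. This avoids entering nearly the same information twice.

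The cost is two sentences and 4 degrees of freedom with two levels per factor, or 1 + 2 + 2 + 2 = 7 with three levels for age, obesity and fibre, out of about 120. The sample size need not change, and no new data are needed, because all four factors must be known before a patient can be randomised.

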5.4. Intervention

Participants will be randomly assigned, in a 1:1 ratio, to one of two groups:

Intervention group: Mediterranean diet without red and/or processed meat

They will receive motivation and behavioural support through the use of the mobile application, which will provide them with reminders to self-monitor their changes in eating; while the rest of the clinical care will be usual. After randomization of the patients, the research team will give them more information about the use of the mobile app, with specific

indications to avoid red and processed meat in the context of a healthy Mediterranean dietary pattern, taking into account the key elements proposed in the dietary guidelines for CVD prevention. The app will provide details of Mediterranean diet recommendations, as well as recipes, tips and alternatives to replace meat when cooking at home or eating out. Participants will record their daily diet through the mobile application, during the first and last week of the intervention. The rest of the clinical care will be usual.

Control group: Mediterranean Diet

Similarly, the control group will be helped to download and use the mobile application, although they will only have access to a restricted version of it, by which they will receive brief and general information to maintain a healthy lifestyle following the general guidelines on the Mediterranean diet (without specific recommendations to reduce red and processed meat). Participants will also record their daily diet through the app, during the first and last week of the intervention. The rest of the clinical care will be usual.

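### Baseline observation carried forward is a weak missing-data check here: if dropout differs by arm, it can shift the sensitivity estimate for LDL-C with no true effect

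*Protocol*

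**What the plan says.** The main analysis in section 5.7 is an observed-case comparison: "The analysis of effectiveness measures will use data from all participants for whom a baseline and monitoring measure exists". The model is a linear regression "with adjustment of the initial values of the dependent variable and the place of recruitment".

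Missing main-outcome values are then addressed in a sentence that begins "A second sensitivity analysis will use the techniques of" and names two methods. One is "baseline observation carried forwards", defined as substituting the participant's initial value. The other is multiple imputation based on allocated group and participant characteristics. The change log shows that both were added in version 1.1. Section 5.7 gives no rationale for assuming zero change and does not say how a disagreement between the two methods would be read.

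On the comparator, section 5.4 says control participants get brief general information "following the general guidelines on the Mediterranean diet". Section 5.1 describes the same arm as receiving general advice to lower saturated fat, and section 2 states that lowering saturated fat reduces LDL-C. Dropout is given once, in section 5.7, as 20% overall.

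**The concern.** Carrying the baseline forward is often defended as cautious because it credits dropouts with no benefit. That defence works best when the comparator is not expected to change. Here the protocol's own reasoning makes some LDL-C fall plausible in both arms. A fixed zero then removes improvement from each arm in proportion to its dropout, and the arm that loses fewer people looks better.

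Unequal dropout is also plausible. Participants are not blinded (section 5.5), and app support differs: prompts, recipes and tips in one arm, a restricted version in the other (section 5.4).

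What is at stake is how useful the robustness check is. As described, the planned multiple imputation works under missing at random. Carrying forward is therefore the only planned look at a departure from that assumption, and it examines a single, undefended point while adding no uncertainty for the filled-in values.

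**Working it through.** **Inputs from section 5.7.** 78 per arm; target difference 15 mg/dL; SD 26 (the cited trial "showed a long-term change in LDL-C of approximately 15 mg/dL (SD26"); power 90%; α 0.05, taken as two-sided; dropout 20% overall.

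**Assumptions, not in the protocol.** Common mean LDL-C change of −5, −10 or −15 mg/dL; dropout of 20%/20%, 15% v 25% or 10% v 30%; dropout random within arm; baseline SD 18; change independent of baseline.

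**The plan's own figure.** n = 2(1.96 + 1.28)² × 26²/15² gives 64 per arm; the t-test version gives 65. Then 65 × 1.2 = 78, as stated. The inputs are therefore read correctly.

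**Shift.** Let m be the mean change dropouts would have shown, the same in both arms. Setting it to zero removes m·d1 from the intervention mean and m·d0 from the control mean, so the error in the arm difference is m(d0 − d1). It is zero only if m = 0 or d0 = d1.

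- m = −10, d1 = 0.10, d0 = 0.30: −10 × 0.20 = −2.0 mg/dL, a false benefit.
- m = −15, same dropout: −3.0 mg/dL.
- Rates reversed: +2.0 and +3.0 mg/dL, a false harm.

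**Standard error.** The variance of the carried-forward change in an arm is (1 − d)·26² + d(1 − d)·m². For m = −10:

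- d = 0.10: 608.4 + 9.0 = 617.4
- d = 0.30: 473.2 + 21.0 = 494.2
- SE = √[(617.4 + 494.2)/78] = 3.8

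With complete data, SE = √(2 × 676/78) = 4.2. For observed cases at 10% v 30%, SE = √(676/70.2 + 676/54.6) = 4.7. Losing a fifth of the outcomes thus yields an apparently more precise estimate than losing none.

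**Size of the carried-forward test by hand (m = −10, 10% v 30%).** 2.0/3.78 = 0.53; P(Z > 1.43) + P(Z < −2.49) = 0.076 + 0.006 ≈ 8.3%.

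**Simulation.** Baseline-adjusted regression with no true effect, 4,000 runs per case. Ranges cover both directions of the dropout gap.

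| Common fall (mg/dL) | 15% v 25%: shift | test size | 10% v 30%: shift | test size |
|---|---|---|---|---|
| 5 | 0.5 | 5.0–5.8% | 1.0 | 5.3–6.1% |
| 10 | 1.0 | 5.7–5.9% | 2.0 | 8.3–8.7% |
| 15 | 1.5 | 6.8–7.0% | 3.0 | 12.8–13.4% |

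At 20%/20% the shift is 0 and the size 5.0–5.1%. The observed-case analysis stays at 4.3–5.7% throughout. Simulation error is about ±0.7 points, so the first row is hardly distinguishable from 5%.

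**With a true effect of −15** (control −10, intervention −25; 2,000 runs), the expected carried-forward estimate is −25(1 − d1) + 10(1 − d0):

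- 20%/20%: −20 + 8 = −12.0
- 10% intervention v 30% control: −22.5 + 7 = −15.5
- 30% intervention v 10% control: −17.5 + 9 = −8.5; this test then rejects in 57% of runs, against 89% for observed cases.

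**The case against.** Four counter-arguments deserve weight.

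**No decision rests on this test.** It is one of two sensitivity techniques, and the primary inference is the observed-case regression. This stands in full. A reader might infer from the 8–13% figures that the trial's type I error is inflated, or that this analysis could confirm a false result or overturn a true one. The documents do not support that: section 5.7 gives no rule by which a sensitivity analysis changes the conclusion, and the figures describe only the carried-forward test taken alone.

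**The shift is an error only if dropouts improve.** If people who leave the programme stay at baseline, m = 0 for them and the filled-in mean is right. This also stands. The protocol neither states nor argues it, however, and a method fixed at that one point cannot show what happens elsewhere.

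**The numbers are modest and conditional.** A 20-point dropout gap and a 15 mg/dL fall in controls are the severe end; that fall equals the whole difference the trial hopes to detect. At 15% v 25% with a 10 mg/dL fall, the shift is 1 mg/dL and the size about 6%. Even 3 mg/dL is one fifth of the target.

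**Control-based imputation also shrinks a true effect.** If intervention dropouts take the control mean at 20% dropout, −15 becomes 0.8 × −15 = −12. That is true, but with no treatment effect the control mean is the right mean for both arms, so unequal dropout alone creates no difference.

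The unseen SAP may hold further missing-data detail. The choice of carrying forward is nonetheless fixed in the protocol.

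**Conclusion.** The point holds as a minor improvement to a sensitivity analysis. If dropouts improve to some degree and dropout differs by arm, the carried-forward estimate moves by m(d0 − d1) with no true effect: 0.5 to 1.5 mg/dL at 15% v 25% and 1 to 3 mg/dL at 10% v 30%, for falls of 5 to 15 mg/dL. Its standard error understates uncertainty because the filled-in values carry none.

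It would be too strong to call the method anti-conservative in general. At equal 20% dropout it only attenuates. Heavier control dropout favours the intervention; heavier intervention dropout works against it. Because the direction depends on which arm loses more, the method cannot be relied on as conservative. The main analysis and its type I error are untouched.

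All sizes rest on assumed dropout by arm and an assumed common change, neither of which the protocol gives.

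**What to change.** In section 5.7, replace baseline carried forward with delta-adjusted (tipping-point) or control-based multiple imputation, built on the imputation already planned, as the check on departures from missing at random. Carrying forward may stay as a descriptive supplement. Report dropout by arm; section 5.6 already lists the completion rate as a process measure, so no new data are needed.

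A common delta added to dropouts in both arms moves the estimate by δ(d1 − d0). Carrying forward corresponds, in its mean, to one such value: with a 10 mg/dL fall, δ = +10 at 10% v 30% gives 10 × (0.10 − 0.30) = −2.0 mg/dL. The delta analysis shows that case within a declared range, alongside milder ones, and carries imputation uncertainty.

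The cost is one protocol sentence, a little extra analysis, and the need to choose and justify the delta range in advance; that detail can sit in the SAP.
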